1.1 Study Background

1.1.1 Peripheral Artery Disease

Peripheral artery disease (PAD) is the third leading cause of cardiovascular morbidity, following coronary artery disease and stroke ^{1,2}. PAD occurs with the progression of atherosclerosis in lower extremity arteries. Patients with PAD classically present with claudication, but can also present with decreased exercise capacity and progressive functional impairment ³⁻⁶. These symptoms are thought to result from the following potential mechanisms: lower extremity atherosclerosis and arterial obstruction leading to skeletal muscle ischemia and impaired cellular metabolism, mitochondrial dysfunction leading to the production of reactive oxygen species as well as free radicals, and subsequent endothelial dysfunction leading to impaired vasodilation and decreased hyperemia in the setting of increased metabolic demand ³⁻⁵.

The goals of therapy for PAD patients are to maximize their exercise capacity, improve their functional status, and improve their quality of life ⁵⁻⁹. The standard therapies for symptomatic PAD are symptom-based exercise therapy and revascularization if indicated ⁵⁻⁹. The exercise protocol for PAD patients that is recommended by clinical practice guidelines and has become standardized in clinical investigations is based on leg symptoms: walk at a constant speed (on a treadmill if possible) until there is mild to moderate claudication, rest until the pain has completely ceased, resume walking at the same speed, and increase the speed when one can walk 8 minutes without stopping for leg symptoms ⁵⁻⁹. This exercise protocol is performed for 45 consecutive minutes, 3 to 5 days a week ⁵⁻⁹. The benefits of exercise in PAD patients include increased vasodilation which leads to improved skeletal muscle perfusion as well as metabolism, enhanced mitochondrial function, and improved endothelial function ⁵⁻⁹.

PAD exercise programs can occur in a supervised setting or at home ⁶⁻⁹. Supervised exercise programs utilize treadmill walking under the direct supervision of an exercise physiologist or a physical therapist who enforces the standard symptom-based exercise protocol ⁷. There is substantial evidence demonstrating the effectiveness of supervised exercise programs for patients with symptomatic PAD ¹⁰⁻¹⁶. However, Medicare and most private health insurance companies do not provide coverage for supervised exercise programs, limiting the feasibility of supervised exercise for most patients ^{5,17}.

In contrast, home exercise programs offer an alternative treatment strategy that is more feasible for patients. Home exercise programs have also demonstrated significant efficacy of improving maximal walking ability for symptomatic PAD patients ¹⁷⁻²⁴, and are based on the standard symptom-based exercise protocol without direct supervision ^{5-9,17-24}. Limitations to home exercise programs include the inability to objectively monitor exercise capacity at home in the absence of a treadmill, variable adherence rates to the standard protocol in the absence of direct supervision, and variable adherence rates to the performance of exercise for 45 minutes, 3 to 5 days a week, in the absence of a supervised program. In order to address these limitations, several investigators have studied the utilization of a fitness monitor during symptom-based home exercise sessions ¹⁷⁻²¹.

1.1.2 Daily Step-based Exercise Therapy

The recommended exercise goal for cardiovascular disease prevention is 10,000 steps a day ²⁵. On the other hand, a daily step count less than 5,000 has been associated with a negative impact on health ²⁶. Prior studies have explored the efficacy of step-based exercise therapy using fitness monitors on improving health in both patients with chronic disease and the adult population in general ^{27,28}. There are ongoing studies examining the effectiveness of step-based exercise therapy on improving cardiovascular health ^{29,30}. The effect of step-based exercise therapy using fitness monitors has not been studied in patients with symptomatic PAD.

In the current digital era, fitness monitors have sensors that can accurately and reliably measure the number of steps walked, distance walked, time of physical activity, and sedentary time ³¹⁻³³. Given their affordability and their ability to measure these data points on a real-time basis, fitness monitors have

become a popular exercise accessory for the general population as well as patients with chronic disease³³⁻³⁵. Step-based exercise therapy using fitness monitors have the potential to improve human health through several different mechanisms. First, the quantification of exercise allows patients to set objective goals, self-monitor their progress, and modify their physical activity based on real-time data points³³. In addition, fitness monitors are worn easily without limiting activities of daily living³³. This allows patients to wear them 24 hours a day, and can facilitate potentially higher adherence rates to exercise. Finally, fitness monitors have the potential to promote behavior changes that are typically used in clinical behavioral interventions³⁶.

1.2 Study Rationale and Aim

The **E**ffectiveness of **D**aily **S**tep-based **E**xercise **T**herap**Y** Using **F**ITness **M**onitors for **P**eripheral **A**rtery **D**isease (**EASY FIT**) Trial will be a single-center prospective non-inferiority randomized controlled trial comparing the efficacy of a novel 12-week daily step-based exercise program vs. the efficacy of a standard guideline-recommended symptom-based exercise program, on improving walking ability in patients with symptomatic lower extremity peripheral artery disease (PAD). We will enroll and randomize 40 patients to a novel 12-week step-based exercise program or a standard guideline-recommended 12-week symptom-based exercise program. To date, we believe that our study is the first to investigate the efficacy of a 12-week daily step-based exercise program on improving walking ability in patients with symptomatic lower extremity PAD. As such, our clinical investigation is a pilot study and will aim to assess the efficacy, safety, and feasibility of a novel daily step-based exercise program for this particular patient population. We believe that this pilot study will generate data for a larger trial in the future.

Compared to the standard guideline-recommended symptom-based exercise program, we hypothesize that a daily step-based exercise program using fitness monitors will be non-inferior in improving walking ability and quality of life for patients with symptomatic lower extremity PAD. We also hypothesize that a daily step-based exercise program will be safe and feasible.

1.3 Study Benefits and Risks

1.3.1 Study Benefits

The potential benefits of a daily step-based exercise program include increased walking ability and exercise capacity (as demonstrated by increased daily walking distance and increased daily time of physical activity), decreased sedentary time, improved quality of life, improved cardiovascular health, and improved general health.

1.3.2 Study Risks

The potential risks of a daily step-based exercise program and a symptom-based home exercise program are exercise-induced events: physical injury, myocardial infarction, and sudden cardiac arrest. The risk of a myocardial infarction during a cardiac rehabilitation exercise program is approximately 0.00013% or 1 event per 752,365 patient-exercise hours³⁷. The risk of sudden cardiac arrest during a cardiac rehabilitation exercise program is approximately 0.00045% or 1 event per 219,970 patient-exercise hours³⁷. Habitual exercise has been found to decrease the relative risk of sudden cardiac arrest³⁸.

1.3.3 Study Benefit-to-Risk Ratio Conclusion

Based on the large potential for benefit and the very small probability of adverse risk to the study population, we believe that this study has a favorable benefit-to-risk profile.

1.4 Study Funding

In August 2016, we were awarded an NC TraCS Pilot Grant (#2KR821606) for the execution of this study.

2. **Study Objectives**

2.1 **Primary Endpoint**

The primary endpoint will be the change in the mean daily walking distance over 7 consecutive days between baseline (prior to the exercise program) and after 12 weeks of the exercise program.

2.2 **Secondary Endpoints**

The secondary endpoint will be the change in quality of life between baseline (prior to the exercise program) and after 12 weeks of the exercise program. We will assess quality of life with 2 surveys that have been validated in PAD patients: the Peripheral Artery Questionnaire (PAQ) and the Vascular Quality of Life Questionnaire (VascuQol).

2.3 **Safety Endpoints**

The safety endpoint will be the occurrence of physical injury, myocardial infarction, or sudden cardiac death at 12 weeks.

3. Study Population

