3.3 Study Drop-Out Criteria

Every 4 weeks of the 12-week exercise program and every 4 weeks of the 9-month extension phase: the study investigators will conduct phone calls and chart review for all enrolled patients to assess for any drop-out criteria and adverse events.

Patients will be prematurely discontinued from the study if they develop any of the following drop-out criteria (identical to the exclusion criteria):

1. Wheelchair bound
2. Use of a walking aid (e.g. cane, crutch, walker)
3. Below or above the knee amputation
4. Leg pain at rest
5. Acute or critical limb ischemia
6. Ischemic ulceration or gangrene
7. Diabetes mellitus complicated by neuropathy
8. Walking impairment due to another cause than PAD
9. Ongoing evaluation for coronary artery disease (e.g. awaiting a stress test or cardiac catheterization)
10. Angina with CCS class 3-4 symptoms
11. Active coronary artery disease or ischemic heart disease requiring the initiation or uptitration of an anti-anginal medication
12. Myocardial infarction in the last 3 months
13. Congestive heart failure with NYHA class 3-4 symptoms
14. Active congestive heart failure requiring the initiation or uptitration of diuretic therapy
15. Active arrhythmia requiring the initiation or uptitration of an anti-arrhythmic medication
16. Severe valve disease, or valve intervention in the last 12 months
17. Active cancer or malignancy (not in remission)
18. End-stage renal disease requiring dialysis
19. Advanced liver disease (defined as cirrhosis)
20. Thyroid disease with abnormal TSH in the past 3 months
21. Severe cognitive dysfunction (defined as dementia)

Patients will be prematurely discontinued from the study if they develop any of the following adverse events:

1. Physical injury
2. Myocardial infarction
3. Sudden cardiac arrest

4. Study Design

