4.2.4 Intervention Group

The intervention group will receive the following 12-week step-based exercise prescription. The exercise goal of 5,000 daily steps is based on prior evidence demonstrating that a daily step count of less than 5,000 is associated with a negative impact on health²⁶.

- Week 1: walk at least 3,000 steps every day.
- Week 2: walk at least 3,500 steps every day.
- Week 3: walk at least 4,000 steps every day.
- Week 4: walk at least 4,500 steps every day.
- Weeks 5-12: walk at least 5,000 steps every day.

4.3 **Follow-up**

The study follow-up period will be 14 weeks. Week 1 will be a baseline assessment period during which we obtain baseline data. Weeks 2 through 13 will be the period of the study intervention. Week 14 will be the endpoint assessment period during which we obtain endpoint data.

Week 1

Discussed in Section 5.1 (Study Assessments, Baseline Assessment Period)

Weeks 2 to 13

Every 4 weeks of the 12-week exercise program: the study investigators will conduct both chart review and phone calls for all enrolled patients to assess for any drop-out criteria and adverse events. In addition, the study investigators will instruct patients regarding any concerning symptoms that should be reported to the study team or should require emergent medical attention (by calling 911). In order to assess compliance to the study protocol, all patients will transmit data from their fitness monitors to their online Fitbit accounts every 4 weeks.

Week 14

Discussed in Section 5.2 (Study Assessments, Endpoint Assessment Period)

5. Study Assessments

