8.4 Study Stopping Rules

The study will be prematurely stopped if the study intervention (a daily step-based exercise program) is associated with an increased risk of adverse events and/or harm to patients.

9. Appendices

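### Limb deterioration and cardiac worsening that end a patient's participation count in no safety outcome and are not compared by arm

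*Combined protocol and SAP*

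**What the plan says.** - **Safety endpoint (Section 2.3).** "The safety endpoint will be the occurrence of physical injury, myocardial infarction, or sudden cardiac death at 12 weeks". No other safety outcome is defined.
- **Recognised risks (Section 1.3.2).** These are "exercise-induced events: physical injury, myocardial infarction, and sudden cardiac arrest". The third item is arrest, whereas 2.3 has death.
- **Two lists (Section 3.3).** The first has 21 drop-out criteria, any of which ends participation. Limb items 3-6 are amputation, rest pain, "Acute or critical limb ischemia", and ulceration or gangrene. Cardiac items 10, 11 and 13-15 cover CCS 3-4 angina, NYHA 3-4 heart failure, and coronary disease, heart failure or arrhythmia that needs treatment started or increased, for example "Active congestive heart failure requiring the initiation or uptitration of diuretic therapy". The second list, headed as adverse events, has three entries: injury, infarction and sudden cardiac arrest.
- **Ascertainment (Sections 3.3, 4.3, 5.1 and 5.2).** Phone calls and chart review every 4 weeks, and at the end of Weeks 1 and 14, "assess for any drop-out criteria and adverse events".
- **Hypothesis (Section 1.2).** "We also hypothesize that a daily step-based exercise program will be safe and feasible". No criterion for safety is given.
- **Analysis (Section 6).** All outcomes are by intention-to-treat. Drop-out reasons are not tabulated or compared by arm.
- **Stopping (Section 8.4).** The study stops if the step program is "associated with an increased risk of adverse events and/or harm to patients". Neither term is defined and there is no threshold. Section 8.3 plans no independent monitoring committee.

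**The concern.** A step-arm patient who develops critical limb ischemia, or heart failure that needs more diuretic, leaves the study under 3.3. On the plan's definitions that patient adds nothing to the safety endpoint and has none of the three named adverse events. Section 6 asks for no comparison in which the event would appear.

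The trial enrolls patients with symptomatic lower extremity PAD, makes safety a stated aim, and is meant to inform a larger trial. A safety result that names no form of limb deterioration answers that aim incompletely. An imbalance between arms in limb or cardiac drop-outs could occur and the planned report would not show it.

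**Working it through.** **1. Where each type of event is counted**

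| Event | Safety endpoint (2.3) | Adverse-event list (3.3) | Drop-out list (3.3) | By-arm analysis of drop-outs (6) |
|---|---|---|---|---|
| Physical injury (undefined) | yes | yes | no | not planned |
| Myocardial infarction | yes | yes | yes (item 12) | not planned |
| Sudden cardiac death | yes | not named | no | not planned |
| Sudden cardiac arrest, survived | no | yes | no | not planned |
| Limb deterioration, items 3-6 | no | no | yes | not planned |
| Cardiac worsening, items 10, 11, 13-15 | no | no | yes | not planned |

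The last two rows are the gap. The fourth row is a separate inconsistency: a survived arrest is a listed adverse event but not an endpoint event.

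**2. The plan's own event rates (Section 1.3.2)**

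The stated percentages reproduce:
- infarction: 100 / 752,365 = 0.00013% per patient-exercise hour
- arrest: 100 / 219,970 = 0.00045% per patient-exercise hour

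The documents give no exercise hours for the step arm. Assume 45-minute sessions on 3 to 7 days a week for 12 weeks in 20 patients.
- 3 days: 0.75 x 3 x 12 x 20 = 540 h. Infarctions 540 / 752,365 = 0.0007; arrests 540 / 219,970 = 0.0025; together about 0.003.
- 7 days: 0.75 x 7 x 12 x 20 = 1,260 h. Infarctions 0.0017; arrests 0.0057; together about 0.007.

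Exercise-related cardiac events should therefore add almost nothing to the endpoint. These rates cover exercise hours in cardiac rehabilitation only. The endpoint also counts infarctions and sudden deaths outside exercise, for which the documents give no rate.

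**3. Chance that an uncounted event occurs**

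The documents give no rate for the limb and cardiac items, so the 12-week risk p is an assumption. For 20 patients, P(at least one) = 1 - (1 - p)^20.
- p = 2%: 1 - 0.98^20 = 33%
- p = 5%: 1 - 0.95^20 = 64%
- p = 10%: 1 - 0.90^20 = 88%

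**4. Precision with 20 per arm**

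Zero events in 20 leaves a one-sided exact 95% upper limit of 1 - 0.05^(1/20) = 13.9% (two-sided: 1 - 0.025^(1/20) = 16.8%). This holds for any event definition, including a wider one. It says how wide the intervals will be, not whether the definition is right.

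**5. Effect on the primary design**

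The 90% power in Section 6 uses the 500-step margin, the assumed difference of -350, the SD of 161 and 20 per group. The standard error is 161 x sqrt(2/20) = 50.9, and (500 - 350) / 50.9 = 2.95. At one-sided alpha 0.05 (assumed, since none is stated), the normal approximation gives 90.3%. No safety quantity enters, so a descriptive safety outcome leaves sample size and power unchanged.

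**The case against.** **The events are already looked for, and this is a pilot.** Both are true. Every call and chart review covers the drop-out criteria, so nothing suggests that the events would go undetected. What remains is that no outcome counts them and no analysis compares them.

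**The stopping rule is wider than the endpoint.** This also stands. A reader might infer that 8.4 shuts out limb and cardiac drop-outs, but its wording extends to harm as well as adverse events and could cover them. Harm is undefined, however, and 8.4 does not bring these events into the endpoint or Section 6.

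**The conditions are not shown to be harms of walking.** A reader might infer that they are expected consequences of the program. The documents do not say so: 1.3.2 names three exercise-induced risks, 1.1.1 describes vascular benefit from exercise, and 3.2 groups the limb items as conditions limiting participation. The case for counting them does not need causation. A comparison between randomized arms allows for natural progression.

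**The arms are not shown to differ in ischemic exposure.** It is tempting to argue that the step arm carries more limb risk because only controls are told to rest for pain. But controls are also told to walk until pain reaches 3 or 4 on a 5-point scale and then repeat (4.2.3, 9.2). The step arm has a whole-day count, and nothing forbids rest (4.2.4, 9.3). The documents do not show which arm has the greater exposure.

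**Conclusion.** The concern holds as a gap in endpoint definition and reporting. Followed exactly, the plan would address its safety hypothesis without counting limb deterioration (items 3-6) or cardiac worsening short of infarction or sudden death (items 10, 11, 13-15), and without comparing either by arm. This rests on reading 3.3 as written, with drop-out criteria and adverse events as separate lists and physical injury not stretched to cover the limb items.

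The size cannot be fixed from the documents. The 33% to 88% chance of at least one uncounted event among 20 patients depends entirely on the assumed 2% to 10% risk.

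A reader might also infer that the program would be declared safe despite such events. That goes too far, because the plan has no rule for declaring safety. Nor does the 13.9% limit show that the endpoint is wrongly defined; it reflects 20 patients per arm. The mismatch between sudden cardiac death and sudden cardiac arrest is a plain inconsistency that needs reconciling. The point is worth acting on because the remedy is cheap, not because a harm has been shown.

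**What to change.** 1. In 2.3 and Section 6, add a second safety outcome made up of drop-out items 3-6, 10, 11 and 13-15, exactly as worded in 3.3. Report counts with exact confidence intervals per randomized arm, from the calls and chart reviews already planned.
2. State that patients are discontinued at the first criterion met, so these are first-event counts. No follow-up after discontinuation is described, and later events may be missed.
3. Reconcile sudden cardiac death in 2.3 with sudden cardiac arrest in 1.3.2 and 3.3, and say how a survived arrest is counted.
4. In 8.4, clarify whether harm to patients covers the limb and cardiac drop-out events.

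The cost is protocol wording and one table, with no new visits or data sources and no change to sample size or power. The reported event rate will be higher and will include natural disease progression, for which the control arm gives the comparison. With 20 per arm the intervals will be wide, so the table should be presented as descriptive.

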3.1 Inclusion Criteria

Patients are eligible for enrollment if they meet all of the following criteria.

1. Male or female with an age of 18 years or older
2. Diagnosis of lower extremity PAD, based on at least 1 of the following criteria:
 - Ankle-brachial index (ABI) of 0.9 or less in one or both legs
 - Invasive angiography demonstrating obstructive lower extremity artery disease
 - History of prior endovascular or surgical revascularization of lower extremity artery
3. Symptomatic lower extremity PAD characterized by:
 - Fontaine Stage IIa - intermittent claudication after walking > 200 meters
 - Fontaine Stage IIb - intermittent claudication after walking < 200 meters
4. Have a mobile phone with Wifi and Bluetooth capability
5. Have a safe and suitable walking environment (e.g. safe sidewalks next to home)
6. Have the ability to read and speak the English language

3.2 Exclusion Criteria

Patients are not eligible for enrollment if they meet any of the following criteria.

Any health condition that may limit full participation in an exercise program	
1. Wheelchair bound2. Use of a walking aid (e.g. cane, crutch, walker)3. Below or above the knee amputation4. Leg pain at rest5. Acute or critical limb ischemia6. Ischemic ulceration or gangrene7. Diabetes mellitus complicated by neuropathy8. Walking impairment due to another cause than PAD
Any health condition that may be unsafe to participate in an exercise program	
9. Ongoing evaluation for coronary artery disease (e.g. awaiting a stress test or cardiac catheterization)10. Angina with CCS class 3-4 symptoms11. Active coronary artery disease or ischemic heart disease requiring the initiation or uptitration of an anti-anginal medication12. Myocardial infarction in the last 3 months13. Congestive heart failure with NYHA class 3-4 symptoms14. Active congestive heart failure requiring the initiation or uptitration of diuretic therapy15. Active arrhythmia requiring the initiation or uptitration of an anti-arrhythmic medication16. Severe valve disease, or valve intervention in the last 12 months
Any health condition that may influence study outcomes independently	
17. Active cancer or malignancy (not in remission)18. End-stage renal disease requiring dialysis19. Advanced liver disease (defined as cirrhosis)20. Thyroid disease with abnormal TSH in the past 3 months21. Severe cognitive dysfunction (defined as dementia)

3.3 Study Drop-Out Criteria

Every 4 weeks of the 12-week exercise program and every 4 weeks of the 9-month extension phase: the study investigators will conduct phone calls and chart review for all enrolled patients to assess for any drop-out criteria and adverse events.

Patients will be prematurely discontinued from the study if they develop any of the following drop-out criteria (identical to the exclusion criteria):

1. Wheelchair bound
2. Use of a walking aid (e.g. cane, crutch, walker)
3. Below or above the knee amputation
4. Leg pain at rest
5. Acute or critical limb ischemia
6. Ischemic ulceration or gangrene
7. Diabetes mellitus complicated by neuropathy
8. Walking impairment due to another cause than PAD
9. Ongoing evaluation for coronary artery disease (e.g. awaiting a stress test or cardiac catheterization)
10. Angina with CCS class 3-4 symptoms
11. Active coronary artery disease or ischemic heart disease requiring the initiation or uptitration of an anti-anginal medication
12. Myocardial infarction in the last 3 months
13. Congestive heart failure with NYHA class 3-4 symptoms
14. Active congestive heart failure requiring the initiation or uptitration of diuretic therapy
15. Active arrhythmia requiring the initiation or uptitration of an anti-arrhythmic medication
16. Severe valve disease, or valve intervention in the last 12 months
17. Active cancer or malignancy (not in remission)
18. End-stage renal disease requiring dialysis
19. Advanced liver disease (defined as cirrhosis)
20. Thyroid disease with abnormal TSH in the past 3 months
21. Severe cognitive dysfunction (defined as dementia)

Patients will be prematurely discontinued from the study if they develop any of the following adverse events:

1. Physical injury
2. Myocardial infarction
3. Sudden cardiac arrest

4. Study Design

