4.2.2 Fitness Monitor

Both the control group and the intervention group will receive a Fitbit Flex which has been validated for step count measurement. During enrollment, the study investigators will set up the Fitbit Flex for all patients. This set-up process will be the only stage where patients will need to have online access. In order to set up the Fitbit Flex, all patients will need to have a mobile phone with WiFi and Bluetooth capability. The study investigators will download the free Fitbit application onto the mobile phone for each patient, create a free online Fitbit account for each patient, and pair the Fitbit Flex to the mobile application. Once the Fitbit Flex and the mobile application are paired, the Fitbit Flex can sync data to the online Fitbit account wirelessly through Bluetooth. Patients will be instructed to sync their Fitbit data to their online Fitbit account every 4 weeks.

The study investigators will have access to all online Fitbit accounts for the study duration (3 months for the primary and secondary endpoints, and 1 year for the exploratory endpoints). There will be no patient-identifying information in any online Fitbit account. Instead, each patient will be assigned a random alphanumeric code, which will be used as the patient name on the online Fitbit account.

At the end of the study, all patients will be allowed to keep their Fitbits at no cost, indefinitely.

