5.2 Endpoint Assessment Period

Week 14 will be the endpoint assessment period and will be structured identically to Week 1, during which both the intervention group and the control group will wear their fitness monitors for 7 consecutive days. In addition to their usual daily activities, all patients will be instructed to walk continuously for at least one extended period of time on a daily basis. Given that this is a pilot study of a novel exercise program in PAD patients, the duration and frequency of these extended periods of time will be at the patients' discretion.

At the end of Week 14: the study investigators will conduct both chart review and phone calls for all enrolled patients to assess for any drop-out criteria and adverse events. In addition, the study investigators will instruct patients regarding any concerning symptoms that should be reported to the study team or should require emergent medical attention (by calling 911). Both groups will transmit the data from their fitness monitors to their online Fitbit accounts. Finally, both groups will also complete quality of life surveys (PAQ and VascuQol).

6. Statistical Analysis

The primary endpoint of the mean daily walking distance (in steps) over 7 consecutive days will be assessed at baseline and at 3 months. Mean improvement in steps walked from baseline to 3 months will be calculated separately for the intervention and the control group. Noninferiority of the intervention group will be assessed by comparing mean improvement in steps walked, using a 1-sided t-test with a margin of noninferiority of 500 steps. Pedometry data from 22 patients with coronary artery disease undergoing 4 month behavioral intervention suggests the mean improvement in steps walked will have a standard deviation of 161 (VanWormer J, Boucher J, Pronk N, Thoennes J. Lifestyle behavior change and coronary artery disease: effectiveness of a telephone-based counseling program. *J Nutr Educ Behav*. 2004 Nov-Dec; 36(6):333-4.). With a sample size of 20 patients per group, we expect 90% power to demonstrate noninferiority of the intervention group (difference in mean improvement of -350 steps, which is within the margin of noninferiority).

The mean difference in the mean daily walking distance between the study groups will be analyzed by multiple linear regression, controlling for baseline mean daily walking distances. All outcomes will be analyzed by intention-to-treat.

7. Data Management

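### Section 3.3 discontinues patients from the study, partly for lost walking ability, and the plan neither assures their Week 14 outcomes nor says how the promised intention-to-treat analysis handles missing ones

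*Combined protocol and SAP*

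**What the plan says.** - **Removal rule (Section 3.3).** For the 21 conditions: "Patients will be prematurely discontinued from the study if they develop any of the following drop-out criteria". The list includes wheelchair dependence, use of a walking aid, amputation, rest pain, limb ischemia and walking impairment from a cause other than PAD. It also includes conditions with no necessary link to walking, such as an abnormal TSH. A second sentence covers physical injury, myocardial infarction and sudden cardiac arrest: "Patients will be prematurely discontinued from the study if they develop any of the following adverse events". Both remove the patient from the study, not only from the exercise program.
- **Endpoint timing (Sections 2.1, 4.3, 5.2).** The primary endpoint needs a 7-day step mean after the program. Section 4.3 says: "Week 14 will be the endpoint assessment period during which we obtain endpoint data". PAQ and VascuQol are completed at the end of that week.
- **Analysis (Section 6).** "All outcomes will be analyzed by intention-to-treat". The term is not defined, and no missing-data method, sensitivity analysis or dropout allowance is given.
- **Nearest provisions for continued data.** Section 4.3: "all patients will transmit data from their fitness monitors to their online Fitbit accounts every 4 weeks". Section 4.2.2: "The study investigators will have access to all online Fitbit accounts for the study duration". Section 5.2: "the study investigators will conduct both chart review and phone calls for all enrolled patients to assess for any drop-out criteria and adverse events". None of these mentions patients already discontinued.

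**The concern.** The endpoint is change in walking, and several removal triggers are themselves a loss of walking. Patients removed under the rule are therefore likely to differ in outcome from those who stay. Intention-to-treat promises a comparison of all randomized patients, but the plan neither assures the Week 14 value for this group nor says what replaces it. With 20 patients per arm, each one lost is 5% of an arm. A 7-day recording or survey not taken in Week 14 cannot be obtained later, and a missing-data method chosen after the results are known carries little weight.

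**Working it through.** **Inputs from Section 6:** 20 per arm, SD of improvement 161, margin 500, planning difference -350, one-sided t-test.

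**Assumptions (not in the documents):** one-sided alpha 0.05, the number lost per arm, and the deficit D, meaning how many steps lower the change of a discontinued patient is than that of those who remain in the same arm.

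**1. The plan's own figure.** SE = 161 × √(2/20) = 50.9. Noncentrality = (500 − 350)/50.9 = 2.95 on 38 df. Power is 89.4% at one-sided 0.05 (90.3% by the normal approximation), so the stated 90% reproduces. At 0.025 it is 81.9% and does not. The 90% counts all 20 per arm as evaluable.

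**2. Shift if only patients with a Week 14 value are tested.** Each arm's full mean equals its retained mean minus (lost/20) × D. Hence

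retained difference = true difference + ((lost in step arm − lost in control)/20) × D.

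**3. Chance of declaring non-inferiority when the true difference in all randomized patients is -500.** Noncentral t, df = 38 − total lost, noncentrality = (retained difference + 500)/(161 × √(1/n₁ + 1/n₂)).

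Worked case, 2 lost in the step arm and 1 in control, D = 500: retained difference = -500 + (1/20) × 500 = -475; SE = 161 × √(1/18 + 1/19) = 53.0; noncentrality = 25/53.0 = 0.47; df = 35; probability 11.9%.

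| Lost, step v control | D = 161 | D = 500 |
|---|---|---|
| equal | 5.0% | 5.0% |
| 2 v 1 | 6.7% | 11.9% |
| 3 v 1 | 8.8% | 23.2% |
| 1 v 2 | 3.6% | 1.8% |
| 1 v 3 | 2.6% | 0.5% |

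At one-sided 0.025 the 2 v 1 row becomes 3.5% and 6.7%, and the 3 v 1 row 4.8% and 14.6%.

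**4. Comparator with complete Week 14 follow-up.** In the same model, simulated with random discontinuation at 10% v 5% and 15% v 5%, the planned t-test on all 20 per arm gives 5.0–5.3% and 5.1–5.7% at these two deficits. The inflation in step 3 therefore comes from losing the values.

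**5. Power when discontinued patients are kept.** Assume 10% discontinued per arm, a true difference of -350, and that 161 describes only retained patients. SD = √(161² + 0.10 × 0.90 × D²), which is 168 at D = 161 and 220 at D = 500. Noncentrality = 150/(168 × √0.1) = 2.82 and 150/(220 × √0.1) = 2.16. Power is about 87% and 68%.

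**The case against.** The best defense is that this is a gap, not a proven contradiction. Discontinuation and intention-to-treat can coexist, since patients without a value can be analyzed as randomized under a stated method. A reader might infer that Section 6 plans a completers-only test. It does not say so, and every figure in step 3 depends on that inference. This stands.

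A reader might also infer that no Week 14 data could exist for these patients. That goes too far. Investigators have access to all Fitbit accounts and patients keep their devices, so someone who goes on wearing and syncing one could supply steps. Safety contact may already be covered, because calls and chart review are for all enrolled patients. Neither provision assures a Week 14 recording or produces a PAQ or VascuQol score, so the gap in steps and surveys remains.

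Frequency is unknown. Section 1.3.2 gives cardiac-rehabilitation rates for two triggers. If all 40 patients exercised 45 minutes, 5 days a week for 12 weeks (an assumption), exposure is 40 × 0.75 × 5 × 12 = 1,800 hours, which implies 1,800/752,365 = 0.002 infarctions and 1,800/219,970 = 0.008 arrests during exercise. Those triggers add almost nothing. Physical injury and the 21 conditions have no stated rate.

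Large deficits would give much larger error rates. But a 1,000-step deficit is 6.2 times the plan's SD, and many triggers need not reduce walking, so the concern should not rest on such cases.

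The trial is a pilot, but it still states a formal non-inferiority test, a margin and a power figure.

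**Conclusion.** The concern holds as an unresolved gap between Sections 3.3 and 6. The rule removes patients from the study on grounds related to the outcome, no passage assures their Week 14 steps or surveys, and no method for missing values is given. Outcome-related missing data are likely but not certain.

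A reader might infer that the bias favors the step program. The documents do not support that: one rule covers both arms, Section 1.3.2 lists the same risks for both programs, and no discontinuation rate is given. Equal loss with equal deficit is neutral, and heavier control loss works against the step program.

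The size is modest at a deficit of one SD (7–9% against a nominal 5%) and material at 500 steps (12–23%), in both cases only if the step arm loses 2–3 patients to control's 1 and only those with a Week 14 value are tested. The case for changing the plan rests mainly on data that cannot be recovered afterward, not on any one scenario.

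**What to change.** Reconcile Sections 3.3 and 6:

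1. In Section 3.3, state separately when a patient stops the exercise program and when a patient leaves outcome follow-up. Leave the clinical criteria, and any decision about walking, as they are.
2. In Sections 4.3 and 5.2, seek Week 14 Fitbit data, PAQ and VascuQol from every randomized patient who is alive and willing. Confirm that the existing calls and chart review continue after discontinuation.
3. In Section 6, analyze all randomized patients as randomized, name the method for missing Week 14 values, and add one simple sensitivity analysis of departures from it. Report discontinuations by arm and reason.
4. Note beside the 90% power that it assumes 20 evaluable patients per arm at SD 161.

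**Cost:** amendment wording, a little more follow-up through devices and calls already in place, and a little more analysis. Power may also fall if retained patients widen the SD: to about 87% or 68% under the assumptions of step 5.
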